1.6 Safety Pharmacology

Peptides used for vaccination studies do not follow standard pharmacokinetics and such data are not likely to be useful to ascertain peptide safety. Previous studies of similar peptide designs have not shown any pharmacological effects upon vital functions. Consequently, pharmacological distribution studies of SurVaxM have not been performed.

Considering the route of administration (i.e., subcutaneous injection), it is very likely that SurVaxM will remain locally at the injection site for a long period and not be systemically available in any significant amount. Much of the peptide will be taken up by antigen presenting cells (APC) locally and then processed for presentation to the immune system. In addition, some fraction will be degraded locally by peptidases to produce clinically insignificant quantities of free amino acids and smaller peptides. Therefore, as with many other peptide vaccines tested to date, SurVaxM should not reach vital organs to directly affect them. Nonetheless every effort has been made to address the safety of SurVaxM through pre-clinical animal toxicity studies.

According to the study entitled "Subcutaneous Repeated Dose Toxicity Study of 012410-2 in C57BL/6 Mice with a Two-Week Recovery (Study No. 20003268)", subcutaneous administration of SurVaxM at a dose of 500 mcg in adjuvant Montanide ISA 51 VG injected with sargramostim every other week for 12 weeks was well tolerated by male and female mice throughout the dosage and recovery periods. Administration of SurVaxM did not cause mortality or adverse signs of toxicity as evaluated by clinical or skin reaction observations, changes in

body weights, ophthalmologic observations, necropsy observation, terminal body weights and organ weights, clinical pathology and histopathological observations.

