1.9.2 Risks Associated with Montanide

SurVaxM (SVN53-67/M57-KLH) will be given together as an injection with Montanide ISA 51. Together these two agents will be injected just under the skin. Montanide helps to stimulate the immune system and keep the SurVaxM confined to the injection site so that it can work locally on the immune system. Montanide ISA 51 has been used extensively in clinical trials of vaccine

treatments and its risks are minor. These risks include: pain at the injection site, which can be treated with pain medicine; local skin irritation (swelling, local skin redness and sometimes itching) at the injection site; flu-like symptoms including muscle and joint aches.

Rarely, necrotizing granulomatous panniculitis with scarring and possible skin ulceration may occur as a result of subcutaneous injection of vaccines containing Montanide ISA 51. In suchy lesions, deep nodularity can occur at injection sites. High frequency ultrasound may be used to evaluate the injection sites of patients who complain of persistent tenderness or induration lasting over 4 weeks after injection to aid in the diagnosis.

If panniculitis is superficial it may affect the vascular supply to the epidermis leading to superficial skin ulceration. The risk of this complication may be minimized by ensuring that vaccine injection is not given too superficially. Patients that experience skin necrosis or ulceration may be treated with intralesional injection of Kenalog (1 ml lof 5 mg/ml solution) at the vaccine injection site approximately 4 weeks after vaccination. The injection site will be reassessed 4 weeks after Kenalog administration and further doses be modified based on clinically determined response. It is possible that intralesional Kenalog could attenuate the desired immunological response to vaccination. If skin ulceration occurs, secondary cellulitis in the area of ulceration is possible. In such cases, microbial culture and appropriate antibiotic therapy may be indicated.

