6.6 Treatment Discontinuation

Upon treatment discontinuation, all end of treatment evaluations and tests will be conducted. All participants who discontinue due to an AE must be followed until the event resolves or stabilizes. Appropriate medical care should be provided until signs and symptoms have abated, stabilized, or until abnormal laboratory findings have returned to acceptable or pre-study limits. The final status of the AE will be reported in the participant's medical records and the appropriate eCRF.

A patient should be withdrawn from study treatment if, in the opinion of the Investigator, it is medically necessary. In addition, patients will be withdrawn from treatment in the case of:

- 1. RANO criteria defined disease progression. In cases where RANO criteria cannot be applied, progression should be based on unequivocal evidence of progressive disease sufficient to require a change in therapy.
- 2. A need for surgery, radiation, or for other anticancer therapy not specified in the protocol.

- 3. Lost to follow-up or noncompliant.
- 4. Pregnancy. Pregnant patients should be followed for the duration of the pregnancy and the outcome of the pregnancy should be documented.
- 5 Death
- 6. Participant voluntary withdrawal
 - a. A participant may withdraw from the study at any time, for any reason. If a participant discontinues treatment, an attempt should be made to obtain information regarding the reason for withdrawal.
- 7. Investigator decision.

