8.1.3 Treatment Completion/Discontinuation

The End of Treatment Visit should be performed within 30 days (\pm 3 days) after last study drug dosing, or prior to initiation of alternate therapies (whichever occurs sooner). Follow-up and documentation of adverse events and concomitant medications should continue through day 30. Specific procedures to be performed at this visit are illustrated in the Schedule of Procedures and Observations (**Table 3**).

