8.1.4 Post-Treatment Follow-up Phase

Patients who discontinue study treatment should be followed for survival with visits or phone contact every 12 weeks (\pm 4 weeks) until death or lost to follow-up.

.

 Table 3
 Schedule of Procedures and Observations

Protocol Activity	Screen	Vaccine Priming Phase ¹			Adjuvant Temozolomide ²	Vaccine Maintenance Phase ³	Disease Assessment	End of Treatment ⁴	Survival Follow-up ⁵	
		V1	V2	V3	V4	Day 1 of each 28 day cycle	Every 12-weeks (± 2 weeks)	Every 8 weeks (± 4 weeks)		Every 12 weeks (± 4 weeks)
Tumor tissue	X									
Medical history	X									
Physical examination	X	X	X	X	X	X	X	X		
Neurological examination/ MMSE ¹⁴										
Vital Signs(to include weight)	X	X	X	X	X	X	X	X		
Karnofsky Performance Status	X	X	X	X	X	X	X	X		
Hematology ⁶	X	X	X	X	X	X	X			
Chemistry ⁷	X	X	X	X	X	X	X			
Urinalysis	X	X	X	X	X					
Pregnancy Test (serum) ⁸	X	X	X	X	X	X				
HLA typing ¹³	X									
Humoral and Cellular Immune Reponses ⁹		X						X	X	
Brain MRI ¹⁰	X							X	X	
Study Vaccine		X	X	X	X		X			

Protocol Activity	Screen	V	accine Pri	ming Phas	e ¹	Adjuvant Temozolomide ²	Vaccine Maintenance Phase ³	Disease Assessment	End of Treatment ⁴	Survival Follow-up ⁵
		V1	V2	V3	V4	Day 1 of each 28 day cycle	Every 12-weeks (± 2 weeks)	Every 8 weeks (± 4 weeks)		Every 12 weeks (± 4 weeks)
Measurement of local reaction 15		X	X	X	X		X			
Adjuvant Temozolomide						X				
Concomitant Medications	X	X	X	X	X	X	X	X	X	X ¹¹
Adverse Events Assessment ¹²		X	X	X	X	X	X	X	X	
Contact Information for survival follow-up										X

Footnotes for Schedule of Procedures and Observations:

Note: Unless otherwise noted, study assessments should be completed prior to dosing at each treatment visit.

- 1. V1 within 7-28 days after completion of chemoradiation and then every two weeks (14 days \pm 3 days) for a total of 4 doses.
- 2. Adjuvant temozolomide therapy (TMZ) will begin ≥42 days after completion of concomitant temozolomide radiation therapy and given for 6 cycles or more (at the discretion of the investigator), or until intolerance or tumor progression. Temozolomide to be taken on Day 1 through Day 5 of each 28-day cycle ± one week window for tests and visit.
- 3. Maintenance Vaccine Phase: SurVaxM should be administered every 12 weeks (± 2 weeks) after the priming phase until intolerance or tumor progression (12-week cycle ± one week window for tests and visit).

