- 4. The End of Treatment visit should be performed within 30 days (± 3 days) after last study drug dosing, or prior to initiation of alternate therapies (whichever occurs sooner). Follow-up and documentation of adverse events and concomitant medications should continue through day 30 (± 3 days), or until lost to death or follow-up.
- 5. Patients who discontinue study treatment should be followed on study for survival, with visits or phone contact every 12 weeks (±4 weeks) until death or lost to follow-up.

- 6. Hematology: CBC with differentials, platelets.
- 7. Chemistry: (CMP) defined as: chloride, CO₂, potassium, sodium, BUN, glucose, calcium, creatinine, total protein, albumin, total bilirubin, alkaline phosphatase, AST, ALT, A/G ratio, BUN/creatinine ratio, osmol (Calc), anion gap.
- 8. Pregnancy test is required for women of child bearing potential only. A serum pregnancy test must be performed during screening. If the serum pregnancy test is not performed within 7 days of dosing on Priming Phase V1-Day 1, a urine pregnancy test must be performed on Priming Phase V1-Day 1 with results reviewed prior to dosing. Testing may be repeated throughout the study as indicated.
- 9. Blood: six 10 mL green top tubes and one 3.5 mL gold top tube to be collected for in vitro immunological assays (see Section 8.2).
- 10. Brain MRIs must be obtained from the postoperative period (ideally with 72 hours) and post-chemoradiation period (within 1-14 days of completion of chemoradiation).
- 11. Subsequent to progression, medication review is limited to new anti-cancer regimens.
- 12. Documentation of adverse events occurring from the date the participant signs the study consent until 30 days after the last intervention or a new treatment is started, whichever occurs first. Any serious adverse event occurring any time after the reporting period must be promptly reported if a causal relationship to study treatment is suspected.
- 13. HLA –A low resolution panel
- 14. MMSE: Mini Mental State Exam will be done at the discretion of the PI. (41)
- 15. Patient to be instructed to check injection site for 24 to 48 hr post injection: staff to call within 3 to 5 days to document any reaction (see **Section 6.1.1**).

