10.3 Follow-Up for Serious Adverse Events

All related SAEs should be followed to their resolution, until the study participant is lost to follow-up, the start of a new treatment, or until the study investigator assesses the event(s) as stable or irreversible. New information will be reported when it is received.

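### In SurVaxM maintenance, the End of Treatment visit and adverse-event window run from the last dose, so progression found after about day 33 makes the visit late and leaves non-serious events after day 30 formally uncounted

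*Combined protocol and SAP*

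**What the plan says.** **Dosing and scans.** Table 3 footnote 3 states that "SurVaxM should be administered every 12 weeks (± 2 weeks) after the priming phase until intolerance or tumor progression". Table 3 sets disease assessment every 8 ± 4 weeks.

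**End of Treatment visit.** Table 3 footnote 4: "The End of Treatment visit should be performed within 30 days (± 3 days) after last study drug dosing", or before alternate therapy if that comes sooner. Section 8.1.3 gives the same rule.

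**End of adverse-event documentation.** Four places set it, and they differ:
- Section 8.1.3: "Follow-up and documentation of adverse events and concomitant medications should continue through day 30".
- Table 3 footnote 4: through day 30 (± 3), with death or loss to follow-up as other end points.
- Table 3 footnote 12, attached to the adverse-event row: "until 30 days after the last intervention or a new treatment is started, whichever occurs first".
- Section 10.1.3: 30 days after the last intervention, with resolution, loss to follow-up, new treatment or a judgement of stability as alternatives.

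**After the window.** Footnote 12 and section 10.2.2 keep suspected-related serious events reportable. The survival follow-up column of Table 3 has no adverse-event assessment.

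**Follow-up of events already recorded.** Section 6.6: "All participants who discontinue due to an AE must be followed until the event resolves or stabilizes". Section 10.3 lets follow-up of related serious events end at loss to follow-up, "the start of a new treatment, or until the study investigator assesses the event(s) as stable or irreversible".

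**The concern.** Both clocks start at the last dose, but in maintenance nobody knows which dose was the last until the patient stops. Patients generally stop at progression, which is found at a scan or clinically and not on a date tied to the previous injection. A 30-day clock suits treatment given every two or four weeks. It does not suit a 12-week interval.

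Two consequences follow. The End of Treatment visit becomes impossible to perform on time through no fault of the site. And whether a non-serious event between day 31 and the stopping date belongs in the data depends on whether the patient later progressed or received another dose. Safety and tolerability is a secondary objective, and the number of Grade 3 or 4 toxicities is a secondary endpoint (section 12.3). Ulceration or necrosis at the injection site is Grade 3 in section 10.1.2.1 but does not by itself meet the definition of serious in section 10.2.1. A rule that makes inclusion depend on progression is a poor basis for counting such events.

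**Working it through.** The plan states no figure here, so the check is calendar arithmetic on its own windows.

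**Inputs**
- Dosing interval: 12 ± 2 weeks = 84 days, range 70 to 98 (Table 3 footnote 3).
- Scan interval: 8 ± 4 weeks = 56 days, range 28 to 84 (Table 3).
- End of Treatment visit: no later than 30 + 3 = day 33 (footnote 4).
- Adverse-event window: day 30, or earlier at new treatment (footnote 12).

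**Step 1: one event, two outcomes.** Take a non-serious ulcer starting on day 45 after a maintenance dose.
- If the next dose is given on day 84, the window runs to at least 84 + 30 = day 114 unless new treatment starts first. Day 45 is inside.
- If progression is found at a day-56 scan and no further dose is given, the window closed on day 30. Day 45 is 15 days outside, and the End of Treatment visit is already 56 − 33 = 23 days late.

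**Step 2: how often the visit rule cannot be met.** Assume discontinuation is spread evenly over the dosing interval. The share after day 33 is (interval − 33)/interval:
- 84 days: 51/84 = 61%
- 70 days: 37/70 = 53%
- 98 days: 65/98 = 66%

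A cruder check uses the nominal calendar. With doses on days 0, 84 and 168 and scans on days 56, 112 and 168 (the last before that day's dose), the scans fall 56, 112 − 84 = 28, and 168 − 84 = 84 days after the preceding dose. Two of the three are past day 33. This assumes scans and doses start together.

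These figures describe visit timing only. They are not rates of missed events.

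**Step 3: does section 1.9.2 show late onset?** It describes treating skin necrosis or ulceration about 4 weeks (day 28) after vaccination, then: "The injection site will be reassessed 4 weeks after Kenalog administration". That is 28 + 28 = day 56, which is 26 days past day 30. But a lesion treated near day 28 already exists then, so its onset is inside the window. What may be lost is its outcome or a later worsening; the latter matters because section 12.8 summarises by worst grade.

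**Step 4: where the conflict between 6.6 and 10.3 bites.** Section 6.6 covers events that cause discontinuation. Section 10.3 covers related serious events. They overlap only when a related serious event causes discontinuation. There, one passage requires follow-up to resolution or stabilisation and the other lets it end at new treatment.

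**The case against.** The strongest reply is that collection does not really stop. Table 3 marks adverse-event assessment at every disease-assessment visit, so a patient found to progress on day 56 would normally be asked about events that day. Section 12.8 puts no 30-day limit on the summaries. Suspected-related serious events remain reportable, and some ulcers could qualify as important medical events. Section 10.1.3 lists resolution as one end point, and section 6.3 wants medication for drug-related toxicity reported whatever the timing.

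Much of this stands, and it limits the point. It does not remove it. Footnote 12 governs the very row marked at the disease assessment, so a site applying it literally would not document the day-45 event while another site would. The serious-event exceptions do not reach a non-serious Grade 3 event. The medication safeguard is weakened by Table 3 footnote 11, which limits review after progression to new anti-cancer regimens.

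A reader might go further and infer that late toxicity of the last dose is generally missed, or that the late Grade 3 rate is shown to be biased downward. The documents do not support either. Day 56 is a reassessment date, and no passage describes ulceration starting after day 30. Section 1.9.2 calls the complication rare, and the phase I injection-site reactions were all grade one (section 1.8.2). The remark in section 1.6 that "it is very likely that SurVaxM will remain locally at the injection site for a long period" is made to argue for low systemic exposure, not delayed injury. Nor does the gap affect every patient's last dose equally: temozolomide appears under Study Drugs in section 1.4, so while its 28-day cycles continue the clock may run from a later dose.

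**Conclusion.** The concern holds in a limited form. In maintenance, the End of Treatment rule cannot be met once progression is found after about day 33. A non-serious event starting after day 30 is then formally outside the documentation window, although it would be inside had another dose followed. The end points for adverse-event follow-up also conflict between sections.

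Under even spacing of stops, 61% of maintenance discontinuations would come too late for an on-time visit (53% to 66% across the permitted intervals). The effect on the Grade 3 or 4 count cannot be computed, because no frequency of late-onset events is given. Only the direction is clear: if such events occur and footnote 12 is applied literally, the count can fall but not rise. The point rests on reading the last intervention in maintenance as the last SurVaxM dose, a term the protocol does not define. It should be corrected, but it does not threaten the primary analysis.

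**What to change.** In section 8.1.3, Table 3 footnotes 4 and 12, and section 10.1.3:
- Time the End of Treatment visit from the decision to discontinue, before new therapy where possible.
- Document all adverse events through the later of 30 days after the last dose and the End of Treatment visit, and flag any that start after new therapy.
- State one set of end points for adverse-event follow-up in all four places, and define the last intervention, including whether temozolomide counts.

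Reconcile section 10.3 with section 6.6 for related serious events that cause discontinuation.

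Asking about late injection-site, allergic or autoimmune events at the existing 12-week survival contact is optional. No passage ties toxicity to a 12-week period, and a telephone contact is a weak basis for grading a skin lesion.

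The cost is protocol wording and matching case-report-form instructions, with no added visit. A few later events will be harder to attribute, which the flag makes visible.

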8.2 Blood Draws for Humoral and Cellular Immune Response

Whole blood samples for humoral and cellular immune response analysis will be collected via venipuncture using six 10 mL green top tubes and one 3.5 mL gold top tube.

Sample collection: Immunological analyses will be conducted on blood samples obtained prior to the patient's scheduled vaccination dosing (i.e., predosing), and at all study follow-up visits as indicated on **Table 3**. (to be drawn on day of priming vaccine one (V 1), with disease assessment every 8 weeks (± 4 weeks), and at progression or end of treatment). On each occasion, approximately 50 mL of blood will be obtained from a peripheral venipuncture and collected in six green top (heparinized) tubes and one 3.5 mL gold top tube. Blood tubes will be kept at room temperature until pickup for processing.

Additional End of Treatment blood draw (optional):

All collected blood samples from within RPCI will be sent from Phlebotomy directly to the RPCI Immunomonitoring Facility for PBMC separations and freezing.

Center for Immunotherapy Immune Analysis Facility Shared Resource Cancer Cell Center (CCC), C-416

> [contact] (office) [contact] (lab)

[contact]

Serum will be separated from whole blood gold top tube and frozen at -70°C. Whole blood will be processed to obtain PBMC and aliquoted into 2-10 cryovials per time-point containing 1 million cells per vial (number of vials is dependent upon cell number recovered: see **Appendix E**). Screw cap polypropylene cryogenic tubes will be labeled with the participant's MR number, participant's initials, participant's study number, clinical study number, protocol time point, dose, and protocol day. The samples will immediately be frozen at -70°C or below until analyzed. Samples collected after hours will be maintained at room temperature and processed within 24 hours in the Immune Analysis Facility (IAF).

A blood intake and inventory log will be maintained in the Immune Analysis Facility (IAF).

In vitro immunological assays will be performed at RPCI as a central immunomonitoring site. Pre-immune serum for baseline anti-survivin and anti-KLH antibody titers and T cell multimer assays will be performed in the Neuro-Oncology lab; cytokine analysis and ELISPOT assays will be performed in the RPCI Immune Analysis Facility (IAF). As noted above six 10 mL green top tubes and one 3.5 mL gold top tube will be processed for these assays. Serum from one 3.5 ml gold top tube will be directed to antibody assessments; PBMC collected from green top tubes (approximately equal to that collected from three tubes) will be designated for multimer studies. Remaining PBMC from green top tubes will be used for cytokine analysis and ELISPOT as well as repeat assays or multimer assay if there is a shortfall of PBMC.

Results will be collected at multiple time points throughout the study as groups of patient samples become available for complete analysis. Data will be reported in spreadsheet (Excel) format to be provided to CRS data management for entry.

NETWORK SITES: Follow directions above for blood sample collection and processing (PBMC isolation procedure: see **Appendix E**). PBMC tubes will be labeled with the Subject ID # (unique to Network patients), initials, the participant's study number, clinical study number, protocol time point, dose, and protocol day. PBMC samples from outside RPCI will be shipped frozen on dry ice via Federal Express Overnight in styrofoam-insulated containers, with delivery on Mon-Fri. NO SATURDAY OR SUNDAY DELIVERY. All samples should be shipped, along with the sponsor-provided shipping log, to the address below with e-mail notification to the Basic Science Co-investigator ([contact]):

Roswell Park Cancer Institute Cancer Cell Center (CCC), C-416 Attn: Immune Analysis Facility – I 259614 [name] [name]

> [contact] (office) [contact]

For additional information regarding the handling of samples please contact RPCI's Immune Analysis Facility Shared Resource at [contact] or [contact].

NOTE: In the event that a network site cannot process PBMC samples, whole blood may be shipped at ambient temperature overnight to the RPCI Immune Analysis Facility (IAF). Samples will be maintained at room temperature and processed within 24 hours.

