13 CORRELATIVE DATA ANALYSIS

13.1 Immunological Assessments and HLA Typing

Immunologic response to vaccine will be used as a secondary measure of vaccine activity. Survivin-specific CD8+ responses, CD4+ helper support, and anti-survivin antibody (humoral) responses will be measured individually by the Immunotherapy Core Facility and Neurooncology Laboratory at Roswell Park Cancer Institute. PBMC and serum will be collected according to the schedule in Table 3. Samples from Network sites will be sent to the Immunotherapy Core Facility at Roswell Park Cancer Institute for processing and analysis. To assess immunologic responses to SVN53-67/M57-KLH (SurVaxM), PBMC will be analyzed using multimer, IFNy ELISPOT and qPCR assays of cytokine expression in CD4+ and CD8+ cells. Antibodies to survivin peptides and KLH in serum will also be measured by ELISA to assess humoral immune responses. Each of these assay methods has unique advantages and currently, there is no uniform consensus as to which of them is the most critical indicator of an immunologic response to peptide vaccines. Flow cytometric analysis with multimers provides a relatively accurate estimation of the frequency of specific antigen-binding T cells, without requiring major in vitro manipulation of the patient's leukocytes. Multimer analysis can also be accomplished using a small blood sample. Therefore, multimer analysis will be used as the primary determinant of immunological response/endpoint. Positive reactivity is defined as survivin-specific CD8+ T cell levels 1% greater than registration baseline.

ELISPOT assays and qPCR analysis of cytokine expression indicate the functional status of the antigen-specific T cells and are important for assessing Type-1 T cell responses, but they require isolation of CD4+ and CD8+ populations by flow cytometry, and hence a larger blood sample than multimer assays. Therefore, IFNγ ELISPOT, qPCR and antibody assays will be used as secondary determinants of the immunological response/endpoint.

Immunological analyses will be conducted on blood samples obtained prior to vaccination and at all study follow-up visits. On each occasion, approximately 50 mL of blood will be obtained from a peripheral venipuncture and collected in six green top (heparinized) tubes and one 3.5 mL gold top tube. Blood tubes will be stored at room temperature until pickup for processing.

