16.3 Confidentiality

Any data, specimens, forms, reports, video recordings, and other records that leave the site will be identified only by a participant identification number (Participant ID, PID) to maintain confidentiality. All records will be kept in a limited access environment. All computer entry and networking programs will be done using PIDs only. Information will not be released without written authorization of the participant.

APPROVED RPCI IRB 9/23/2019

Roswell Park Cancer Institute Study Number: I 259614

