 - 11.3.9. After centrifugation the sample is fractioned as shown in **Figure1** below. (PBMC can be seen as cloudy and white)

[figure not shown]

Figure 1. Before and after centrifugation

- 1.1.1. Using a 10mL pipette, harvest the lymphocyte layer (PBMC/BM-MNC) to ensure maximum recovery draw up as much of the lymphocyte layer as possible (Up to half of the LSM can be collected to ensure maximum recovery). Transfer layer to previously set up centrifuge tubes containing 5 mL of HBSS.
- 1.1.2. Bring up the volume of the lymphocyte/HBSS mixture to 30mL with HBSS. Gently invert the tubes 5-10 times to mix then centrifuge at 600 x G for 10 minutes to pellet the cells.
- 1.1.3. Discard supernatant in waste container and resuspend the pellet in 25mL of HBSS. Centrifuge the tubes at 500 x G for 5 minutes.
- 1.1.4. Discard supernatant and resuspend cells in 5mL of CTL/RPMI wash solution. Then pool the volumes from all 4 tubes into 1 tube for a final volume of 20mL.
- 1.2. Preparing PBMCs for counting and cryopreservation
 - 1.2.1. Combine 20μL of the cell suspension with 20μL of 0.4% Trypan Blue, and perform a cell count using the Bio-Rad TC20 cell counter.
 - 1.2.2. Centrifuge the pooled sample at 500 x G for 5 minutes.
 - 1.2.3. Once the yield has been calculated, determine the number of tubes to freeze down based on the following criteria:
 - 1.2.3.1. Freeze down around 10 million cells/vial, regardless of how low the yield.
 - 1.2.3.2. Vial number ≤ 5 : < 10 million cells/vial
 - 1.2.3.3. Vial number > 5: > 10 million cells/vial

- 1.2.4. Prepare cryovials with labels using LIMS that include the sample id, the protocol number, the sample type, the date, and the cell number, attach one label on the worksheet as a record.
- 1.2.5. After the final spin, discard the supernatant and resuspend the cells in the appropriate freeze down medium.
 - 1.2.5.1. If using CTL freeze down medium, resuspend PBMC/BM-MNC in "C" media at a concentration of 20 million cells/mL. Slowly over a 2 minute time period add an equal volume of CTL "AB" media to the cells.
 - 1.2.5.2. If using 10%DMSO/90%FBS then pipette the appropriate volume of medium to the cells.
- 1.2.6. Aliquot 1.0 mL of the suspension into pre-labeled cryovials.

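### Immune-assay tubes must show time point, dose and protocol day, and no masking is described, so staff reading the immune endpoint may know which samples are post-vaccine

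*Combined protocol and SAP*

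**What the plan says.** Section 8.2 labels the lead institution's cryovials with the medical record number, initials and study number, followed by "clinical study number, protocol time point, dose, and protocol day". PBMC tubes from network sites carry the subject ID plus "initials, the participant's study number, clinical study number, protocol time point, dose, and protocol day". Blood is drawn on the day of the first priming dose before dosing, then with disease assessments about every 8 weeks, and at progression or end of treatment. The first draw is therefore the only pre-vaccine sample.

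On reading, Section 8.2 states that "T cell multimer assays will be performed in the Neuro-Oncology lab", while ELISPOT and cytokine assays are done in the Immune Analysis Facility, which also processes and logs the blood. Section 13.1 adds that "multimer analysis will be used as the primary determinant of immunological response/endpoint" and gives the responder rule: "Positive reactivity is defined as survivin-specific CD8+ T cell levels 1% greater than registration baseline". Section 12.7.1 plans a mixed model for immune response over time, with contrasts between time points.

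Two other passages describe labels differently. Appendix E, step 1.2.4, says: "Prepare cryovials with labels using LIMS that include the sample id, the protocol number, the sample type, the date, and the cell number". Section 16.3 says that specimens leaving a site "will be identified only by a participant identification number".

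**The concern.** The immune endpoint is a change within each patient from the first draw to later draws, in a single-arm, open-label trial. A label that gives time point, dose and day tells anyone who sees it which side of that comparison a tube is on. Flow-cytometry multimer results depend on where the gates are set, and the documents fix no gating rule. If post-vaccine tubes were read even slightly higher than baseline tubes, the difference would enter the estimated change in full. It would not shrink with more patients, and no control group would show the same shift.

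At stake is the protocol's secondary measure of vaccine activity and the analysis of its predictors. Section 12.1 intends the trial's estimates for use in planning larger comparative trials, so an inflated responder rate could carry forward.

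**Working it through.** The documents give no figure on this point to reproduce. The check has two parts.

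**1. Do the documents separate the reader from the time point?**

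- Section 8.2, lead institution: time point, dose and protocol day are on the tube.
- Section 8.2, network sites: the same three items are on the tube.
- Appendix E, step 1.2.4: none of the three, but the date is shown. For one patient, dates give the order of the samples, so this label masks only in part.
- Section 16.3: participant ID only. This protects identity and is silent on time point.
- Sections 8.2, 12.7.1 and 13.1 and Appendix E: no recoding step, no masked gating or reading, no random assay order, and no rule on whether a patient's baseline and later samples share a run.

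The time point is therefore on the tube by instruction, and no written step removes it before the assay.

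**2. What could a reading shift do to the responder rule?**

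Input from the plan: positivity is a rise of 1% over baseline (Section 13.1). Assumptions, none of them in the documents:

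- the 1% means 1 percentage point of CD8+ cells;
- each reading has independent normal error with SD s;
- there is one post-vaccine sample and no true change;
- post-vaccine readings are shifted upward by b points.

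The difference between two readings has SD s√2, so

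P(false responder) = 1 − Φ((1 − b) / (s√2)).

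With s = 0.5, s√2 = 0.707:

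| Shift b (points) | (1 − b)/0.707 | False responders | Expected of 50 |
|---|---|---|---|
| 0 | 1.414 | 7.9% | 3.9 |
| 0.1 | 1.273 | 10.1% | 5.1 |
| 0.25 | 1.061 | 14.4% | 7.2 |
| 0.5 | 0.707 | 24.0% | 12.0 |

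The first row is measurement error alone. The shift adds 2.2, 6.5 and 16.1 percentage points (10.1 − 7.9, 14.4 − 7.9, 24.0 − 7.9).

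The result depends heavily on s. Over shifts from 0 to 0.5 points, false responders run from 0.2% to 7.9% with s = 0.25, and from 17.3% to 31.9% with s = 0.75.

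**The case against.** The strongest reply is that nothing here shows that a reader is unmasked. The Immune Analysis Facility freezes the tubes, and a different laboratory runs the multimer assay. The documents do not describe that hand-off, and the opening of Section 8 sends procedures not defined in the text to institutional SOPs that are not part of these documents. Recoding may happen there. This stands: a reader might infer that the laboratory knows the time point, but the documents support only that it may. If recoding is already practised, the remedy is to write it down.

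Four other stronger readings also go beyond the text:

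- **Appendix E has the same fault.** It does not. Its label omits time point, dose and protocol day, and only the date hints at order. Part of the defect is that two label rules disagree.
- **Samples are assayed piecemeal.** Section 8.2 speaks of groups of patient samples becoming available, but this describes when results are collected. It does not say how runs are composed, and it could equally mean batching.
- **The tests between time points are badly inflated.** With 40 pairs and shifts of 0.1, 0.25 and 0.5 SD of the within-patient change, a two-sided 0.05 paired contrast has noncentrality shift × √40 = 0.63, 1.58 and 3.16, and rejects a true null with probability 0.10, 0.35 and 0.88. The arithmetic is right. But the shifts and the 40 pairs are assumed, and a paired test is not the 1% responder rule, so these figures do not measure the primary immune determinant.
- **Initials on network tubes add to the bias.** They conflict with Section 16.3 on privacy and have no bearing on how a sample is read.

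It is also fair to say that the stated objective is to describe the immune response, and that it ranks as secondary.

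**Conclusion.** The point holds as a gap in protection, not as a demonstrated bias. Section 8.2 puts the time point on the tube, no passage removes or masks it, and both the responder rule and the contrasts depend on the comparison that it reveals, without a control arm. A systematic shift in reading could not be separated from a vaccine effect.

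The documents give neither the size nor the direction of any shift. The rise from about 8% to 10–24% false responders is illustrative. It rests on the assumed SD of 0.5 points, shifts of 0.1 to 0.5 points, a percentage-point reading of the 1% rule, one post-vaccine sample and no true change. With a tighter assay the effect is small; with a noisier one, false positives are already common before any shift.

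Only the secondary immune endpoint and its predictor analyses are affected. The 6-month progression-free survival endpoint, its exact binomial test and n=50 are untouched. The change is worth making because it is specific and cheap, not because the trial's main conclusion depends on it.

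**What to change.** 1. Label assay aliquots with a LIMS sample code only: no time point, dose, protocol day, date, initials or record number. Participant ID should also stay off the aliquot, so that samples cannot be linked within a patient at the bench. Write this same label into Section 8.2 (lead institution and network sites) and Appendix E, step 1.2.4.
2. Let CRS data management, which already receives the results under Section 8.2, hold the key until the multimer readings for that run are locked.
3. Where practical, assay a patient's baseline aliquot in the same run as the post-vaccine aliquot with which it is compared, in random order. Do not wait for the whole series: sampling continues to progression or end of treatment, so that would hold samples indefinitely. Section 8.2 foresees 2 to 10 vials per draw, so baseline aliquots can be reserved for later runs when the cell yield allows.
4. Separately, and as a privacy matter only, reconcile the initials on network tubes with Section 16.3.

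The cost is a code list to maintain, reliance on the LIMS to prevent mix-ups once tubes can no longer be identified by eye, and baseline aliquots held frozen until the first post-vaccine sample. The Immune Analysis Facility both processes samples and runs ELISPOT and cytokine assays, so extending the masking to those assays would also need intake and reading to be separated within that facility.
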